9.8.2. Other Samples for Biomarker Research

The following samples for biomarker research will be collected for the purposes described in Section 9.8, and as specified in [Appendix 4](#), where local regulations allow.

- Whole blood
- Serum
- Plasma
- A maximum of 5 samples may be collected at additional time points during the study if warranted and agreed upon by the investigator and Lilly. If these additional samples are requested, they will be used to further investigate biomarkers that may explain treatment response and resistance mechanisms.

All samples will be coded with the patient number. These samples and any data generated can be linked back to the patient only by the study site personnel.

Samples will be retained at a facility selected by Lilly for a maximum of 15 years after the last patient visit for the study, or for a shorter period if local regulations and/or ERBs/IRBs impose shorter time limits. This retention period enables use of new technologies, response to questions

from regulatory agencies, and investigation of variable response that may not be observed until later in the development of LY3415244 or after LY3415244 becomes commercially available.

Technologies are expected to improve during the 15-year storage period and therefore cannot be specifically named. Existing approaches, including but not limited to flow cytometry, mutation profiling, copy number variability analysis, gene expression assays, multiplex assays may be performed on these samples to assess potential associations between these biomarkers and clinical outcomes.

9.9. Health Economics

Health economics and medical resource utilization parameters will not be evaluated in this study.

10. Statistical Considerations

10.1. Sample Size Determination

The primary objective of this study is to assess the safety and tolerability of LY3415244, thereby identifying and confirming the RP2D of LY3415244 to be administered as monotherapy to patients with solid tumors. The secondary objective is to evaluate PK and any observed evidence of clinical efficacy.

In Phase 1a, the total sample size will be determined by the incidence of DLTs.

With at least 3 patients treated at the RP2D in the dose-escalation phase and additional patients treated at the RP2D in Phase 1b, a total of at least 20 patients can provide adequate precision for the estimated incidence rate of the following quantities of interest: (1) patients having a specified AE or (2) patients showing a response (PR/CR) to treatment. With a total sample size of 20, the 95% confidence interval (CI) is approximately equal to the observed incidence rate $\pm 12\%$ to 24%. Example point estimates of incidence rates and corresponding 2-sided 95% CIs are summarized in [Table JZDA.10.1](#). The values are provided as a reference for estimation rather than a basis of any decision criteria. The RP2D may be revised based on the safety data obtained in the expansion phase (Iasonos and O’Quigley 2013).

Table JZDA.10.1. Estimated Incidence Rate and 2-Sided 95% Confidence Interval

N=20			
Number of Cases	Estimated Rate	95% CI ^a	
		Lower Limit	Upper Limit
0	0.0	0.0	0.17
3	0.15	0.03	0.38
5	0.25	0.09	0.49
10	0.50	0.27	0.73
15	0.75	0.51	0.91

Abbreviations: CI = confidence interval; N = number of patients.

a 95% Clopper-Pearson interval for binomial distribution.

10.2. Populations for Analyses

The following analysis sets will be defined for this study:

Enrolled/Safety population: will include all patients who received any quantity of study treatment, regardless of their eligibility for the study. The safety and efficacy evaluation will be performed based on the first dose of study treatment a patient actually received. This population will be used for all dosing/exposure, safety, and efficacy analyses.

Pharmacokinetic population: will include all enrolled patients from whom a valid assay result (according to laboratory guideline) has been obtained.

Biomarker population: will include the subset of enrolled patients from whom a valid assay result has been obtained. No imputation will be performed for missing data due to the limitation of small sample size.

10.3. Statistical Analyses

Statistical analysis of this study will be the responsibility of Lilly or its designee.

Unless otherwise stated, all CIs will be given at a 2-sided 95% level.

Any change to the data analysis methods described in the protocol will require an amendment only if it changes a principal feature of the protocol. Any other change to the data analysis methods described in the protocol, and the justification for making the change, will be described in the Statistical Analysis Plan (SAP) and clinical study report (CSR). Additional exploratory analyses of the data will be conducted as deemed appropriate.

10.3.1. Safety Analyses

All patients who receive any quantity of LY3415244 will be evaluated for safety and toxicity. AE terms and severity grades will be assigned by the investigator using CTCAE Version 4.0.

Safety analyses will include summaries of the following:

- DLTs: the number of patients who experience any DLTs during Cycle 1 will be summarized by cohort by treatment arm in Phase 1a
- DLT-equivalent: the number of patients who experience any AE that qualifies as a DLT during any period of study will be summarized by the first dose by treatment arm in Phase 1a and by tumor type and treatment regimen in Phase 1b
- AEs, including severity and possible relationship to study drug
- AEs by Medical Dictionary for Regulatory Activities system organ class (SOC) by decreasing frequency of Preferred Term within an SOC
- laboratory and non-laboratory AEs by CTCAE Version 4.0 term, maximum CTCAE grade, and CTCAE Grade 3 and above (regardless of causality and at least possibly related to study treatment)
- changes in vital signs and ECGs

10.3.2. Efficacy Analyses

The study was not designed to make an efficacy assessment. However, any tumor response data will be tabulated for all patients in the enrolled/safety analysis set.

The efficacy endpoints are listed and defined as follows:

Objective response rate (ORR) is the proportion of enrolled patients who have received any amount of either study drug, have at least 1 postbaseline tumor image, and achieved a best overall response (BOR) of confirmed CR or PR.

Duration of response (DoR) is defined only for responders (patients with a confirmed CR or PR). It is measured from the date of first evidence of a confirmed CR or PR to the date of the

first observed radiographically documented PD, or the date of death due to any cause, whichever is earlier. If a responder is not known to have died or have objective progression as of the data inclusion cutoff date, DoR will be censored at the date of the last complete objective progression-free disease assessment.

Time-to-response (TTR) is the time from the date of first study treatment until the first evidence of a confirmed CR or PR.

Disease control rate (DCR) is the proportion of enrolled patients who have a BOR of confirmed CR, confirmed PR, or stable disease (SD).

Progression-free survival is defined as the time from the date of first study treatment until the date of the first observed radiographically documented PD or death due to any cause, whichever is earlier. The censoring is taken in the following order:

- If a patient does not have a complete baseline disease assessment, then the PFS time will be censored at the enrollment date, regardless of whether or not objectively determined disease progression or death has been observed for the patient; otherwise,
- if a patient is not known to have died or have objective progression as of the data inclusion cutoff date for the analysis, the PFS time will be censored at the last complete objective progression-free disease assessment date.

Overall survival, an exploratory objective, is determined from the date of first study treatment until death due to any cause. If the patient is not known to have died at the data inclusion cutoff date for the analysis (or is lost to follow-up), OS will be censored on the last date the patient was known to be alive. This endpoint will be followed up for 12 months after the last patient has entered treatment.

The objective response rate, TTR, DCR, DoR, and PFS will be assessed based on RECIST v1.1 (Eisenhauer et al. 2009) and RECIST v1.1 with confirmatory scan for disease progression (Section 9.1.1).

The estimate of ORR and DCR, and the corresponding CI, will be provided by dose-escalation treatment arm and by expansion according to RECIST v1.1 and RECIST v1.1 with confirmatory scan for disease progression (Section 9.1.1). Time-to-event variables, such as TTR, DoR, PFS, and OS (as an exploratory objective), will be summarized by Kaplan and Meier (1958) method by dose-escalation treatment arm and expansion. Presentations of antitumor activity may include patients enrolled in the dose-escalation phase with the same tumor type and dosing scheme. Individual changes in the tumor burden over time will be presented graphically within a tumor type. Subgroup analysis of interest will be further defined in the SAP.

10.3.3. Other Analyses

10.3.3.1. Patient Disposition

A detailed description of patient disposition will be provided, including a summary of the number and percentage of patients entered into the study, enrolled in the study, and treated as well as number and percentage of patients completing the study, as defined in the SAP, or

discontinuing (overall and by reason for discontinuation). A summary of all important protocol deviations will be provided.

10.3.3.2. Patient Characteristics

Demographic data are collected and reported to demonstrate that the study population represents the target patient population considered for regulatory approval.

A summary of baseline patient and disease characteristics, historical diagnoses, preexisting conditions, and prior therapies will be reported using descriptive statistics.

Other patient characteristics at baseline will be summarized as deemed appropriate.

10.3.3.3. Concomitant Therapy

A summary of prior and concomitant medications will be reported.

10.3.3.4. Treatment Compliance

The number of cycles received, dose omissions, dose delays, and dose intensity will be summarized for the enrolled/safety population.

LY3415244 will be administered at the investigator site, therefore treatment compliance is assured.

10.3.3.5. Pharmacokinetic/Pharmacodynamic Analyses

PK parameter estimates for LY3415244 therapy will be calculated by population PK analysis methods using nonlinear mixed effects modeling. The version of any software used for the analysis will be documented, and the program will meet the Lilly requirements of software validation. It is possible that other validated, equivalent PK software programs may be used if appropriate, warranted, and approved by Lilly global PK/PD management. In addition, selected PK parameters (based on actual sampling times), including C_{max} , time of C_{max} , and AUC may be calculated by noncompartmental analysis methods and/or model simulations. As an exploratory analysis, PK parameter estimates for C_{min} at steady state following repeated dose may be evaluated.

Pharmacokinetic/pharmacodynamic analyses will be conducted to explore exposure-response relationships between LY3415244 concentrations in systemic circulation and various pharmacodynamic measures, such as selected safety outcomes, receptor occupancy, and biomarkers.

10.3.3.6. Biomarker Analyses

Biomarkers related to treatment, immune functioning, mechanism of action of study drugs, and/or cancer will be collected and reported. In addition, the relationship between biomarkers and clinical outcome will be assessed. Biomarker relationships by tumor type, changes in biomarker levels at baseline and over time, and differences among dose levels or exposure will be explored as possible. The pharmacodynamic effect from all patients undergoing pharmacodynamic assessments will be explored (Section 10.3.3.5).

10.3.3.7. Immunogenicity Analysis

The frequency and percentage of patients with preexisting ADA, ADA at any time point postbaseline, and with treatment-emergent ADA positivity (TE ADA+) to LY3415244 will be tabulated. Treatment-emergent ADAs are defined as those with a titer 2-fold (1 dilution) greater than the minimum required dilution if no ADAs were detected at baseline (treatment-induced ADA) or those with a 4-fold (2 dilutions) increase in titer compared to baseline if ADAs were detected at baseline (treatment-boosted ADA). For the TE ADA+ patients, the distribution of maximum titers will be described. The frequency of neutralizing antibodies may also be tabulated in TE ADA+ patients.

The relationship between the presence of antibodies and the PK parameters and PD response including safety and efficacy to LY3415244 may be assessed.

10.3.4. Interim Analyses

In the Phase 1a dose-finding portion of the study, safety, PK, and biomarker data (if available) will be reviewed on a cohort-by-cohort basis during the study, until the MTD and/or RP2D is determined. The purpose of these cohort-by-cohort data reviews is to evaluate the safety data at each dose level and determine if a DLT has been observed. The decision whether to advance to the next dose level will be made following discussion between the investigators and Lilly and will be relayed to the sites prior to patients being treated on the subsequent cohort.

Safety and available PK data will be reviewed during the study to inform dose escalation, modifications to the dose-escalation strategy, or other design elements.

An interim analysis will be performed after all patients in Phase 1a have completed the DLT evaluation period. The Lilly study team will evaluate the data from the interim safety and PK/PD analyses before opening the dose expansion cohorts in Phase 1b. In these interim analyses, early antitumor activity may also be explored.

An expansion-specific safety and efficacy interim analysis will be conducted approximately 24 weeks (6 months) after the LPET for each of the expansion cohorts. These interim analyses may be combined if they are expected to occur within approximately a month of each other. Interim analyses may also be combined with any prespecified safety review or reporting (that is, Trial Level Safety Reviews, Development Safety Update Reviews, or IB update reviews). The expansion-specific safety and efficacy primary analyses will be conducted approximately 52 weeks (12 months) after LPET for each of the expansion(s).

The final overall analysis of Study JZDA will coincide with the safety and efficacy primary analysis of the last expansion.

If it is deemed that enough data have been obtained to assess the primary and secondary objectives, a CSR might be created before the last patient visit. In this case, all data until the data-cutoff date will be used for the analysis of safety, efficacy, PK, and PD biomarkers. All data defined in the protocol will continue to be collected from patients on treatment after data-cutoff date and results will be listed. However, summary tables including data after data-cutoff date will not be created.

11. References

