5.1.1. Dose Escalation Phase

Patients in Cohorts A1, A2, A3, A4, A5, A6, A7, and A8, respectively, will receive doses of 3 mg, 10 mg, 30 mg, 70 mg, 200 mg, 600 mg, 1000 mg, and a dose not exceeding 1500 mg according to an every-2-weeks (Q2W) dosing regimen, provided safety is established in the preceding cohorts (see [Table JZDA 7.1](#)).

After the first patient in Cohort A1 receives the first dose of LY3415244, there will be a delay of 1 week to allow for safety observation before the second and third patients receive LY3415244. There will be no additional delays for subsequent patients.

CCI

Cohorts of patients will be treated with escalating doses of LY3415244 according to a mTPI-2 method until the criteria for reaching the maximum-tolerated dose (MTD) are met (see [Section 7.2.2.1](#)). The RP2D of LY3415244 to be tested in the Phase 1b portion of the study will be identified in Phase 1a. The RP2D may be below the MTD, which may or may not be reached during Phase 1a. For some immuno-oncology compounds that have manageable safety profiles and do not reach a MTD, additional information such as pharmacodynamic markers may be helpful in determining the appropriate RP2D (Agrawal et al. 2016; Parchment et al. 2016). Late toxicities of available data up to 90 days will be considered for RP2D determination.

A 1-cycle (28 days) dose-limiting toxicity (DLT) observation period will apply to all cohorts in Phase 1a.

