5.12.2. Dose-Limiting Toxicity and DLT-Equivalent Toxicities

The definition of the DLTs and the DLT-equivalent toxicities (DETs) is specified in Protocol J1C-MC-JZDA (JZDA), Section of Dose-Limiting Toxicity Determination.

Dose limiting toxicities will be summarized and listed for DLT-evaluable population.

Dose limiting toxicities-equivalent toxicities (DETs) will also be listed and summarized for safety population.

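### The raw by-dose count of DLT-equivalent toxicities compares Phase 1a doses over unequal follow-up at the review that precedes expansion, although late toxicity to day 90 is meant to inform the RP2D

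*Protocol*

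**What the plan says.** Five statements matter here.

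- **Window for late toxicity.** Protocol section 5.1.1 (and 5.1): "Late toxicities of available data up to 90 days will be considered for RP2D determination". Neither section says from what date the 90 days run, or requires any patient to reach day 90.
- **Window for DLTs.** Protocol section 5.1.1: "A 1-cycle (28 days) dose-limiting toxicity (DLT) observation period will apply to all cohorts in Phase 1a".
- **Timing of the review.** Protocol section 10.3.4: "An interim analysis will be performed after all patients in Phase 1a have completed the DLT evaluation period". The same section adds: "The Lilly study team will evaluate the data from the interim safety and PK/PD analyses before opening the dose expansion cohorts in Phase 1b". SAP section 5.18 repeats both provisions.
- **Summary of DLT-equivalent toxicities.** Protocol section 10.3.1: "the number of patients who experience any AE that qualifies as a DLT during any period of study will be summarized by the first dose". SAP section 5.12.2 says only: "Dose limiting toxicities-equivalent toxicities (DETs) will also be listed and summarized for safety population".
- **Basis for the RP2D.** Protocol section 7.2.2.3 leaves the choice to discussion between sponsor and investigators on all the data, with no formula. Table JZDA.4.1 lists DLT-equivalent toxicities among the Phase 1a endpoints of the objective that identifies the RP2D.

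The SAP specifies Kaplan-Meier estimation for time to response, PFS, duration of response and overall survival (sections 5.13.3 to 5.13.5 and 5.13.7). It names no time-to-event or fixed-window method for toxicity.

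**The concern.** The plan treats toxicity after Cycle 1 as relevant to dose selection, and protocol section 7.4 says why: immune-related events may appear months after dosing. The stated by-dose summary of that toxicity cannot compare doses at day 90. A count over any period grows with the time each patient has been watched, and at the pre-expansion review that time differs by dose because each cohort waits for the preceding ones.

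At stake is the reading of late toxicity just before about 80 expansion patients are to receive the selected dose. Two equally toxic doses can show different counts only because one opened later.

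**Working it through.** **The plan's own figure.** The documents give no follow-up time or DLT-equivalent rate for this review, so there is nothing on this point to reproduce. The nearest figures are the Appendix 7 rules, which use DLT counts. Ten cells were recomputed with a Beta(1,1) prior, an interval width of 0.10 and a 0.95 cut-off for DU (all three assumed), and all ten agree. They are not in question.

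**Inputs from the documents.**
- DLT period: 28 days (protocol 5.1.1).
- Late-toxicity window: 90 days (protocol 5.1, 5.1.1).
- Fixed-dose cohorts in sequence: A1 to A7, with A8 optional (protocol 5.1.1).
- Patients per dose: 3 to 10 during DLT assessment (protocol 5.2).

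**Assumptions.** The spacing between cohorts, the hazard and the accrual pattern are not in the documents. Day 90 is counted from first dose. Toxicity is set equal at every dose, so any difference in the results comes from follow-up alone.

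**Step 1: follow-up at the earliest review.** With 7 cohorts and spacing g days, the last patient in cohort k has 28 + g × (7 − k) days.

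| Spacing | A4 | A5 | A6 | A7 |
|---|---|---|---|---|
| g = 28 | 112 | 84 | 56 | 28 |
| g = 56 | 196 | 140 | 84 | 28 |

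Wider spacing helps A5 and A6. A7 stays at 28 days.

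**Step 2: expected proportion with an event, constant hazard.** Let r be the risk per 28 days and λ = −ln(1 − r)/28. If everyone at a dose has d days, the expected proportion is 1 − exp(−λd). For r = 0.10, λ = 0.003763. At 28 days this gives 0.100, and at 90 days 1 − exp(−0.3387) = 0.287.

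Giving every patient the last patient's 28 days is the extreme case. If accrual at the last dose is spread evenly over W days, follow-up runs from 28 to 28 + W, and the expected proportion is

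1 − [exp(−28λ) − exp(−(28 + W)λ)] / (λW).

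For r = 0.10:
- W = 28: 1 − (0.900 − 0.810)/0.1054 = 0.146
- W = 56: 1 − (0.900 − 0.729)/0.2107 = 0.189

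| Risk per 28 days | Last dose, all at 28 days | Last dose, W = 28 | Last dose, W = 56 | Dose with 90 complete days |
|---|---|---|---|---|
| 5% | 5.0% | 7.4% | 9.7% | 15.2% |
| 10% | 10.0% | 14.6% | 18.9% | 28.7% |
| 20% | 20.0% | 28.3% | 35.5% | 51.2% |

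**Step 3: shape of onset.** Fix the 90-day risk P and let onset be Weibull. The expected proportion at 28 days is 1 − exp{ln(1 − P) × (28/90)^s}. Shape s = 0.5 puts events early and s = 2 puts them late.

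| Assumed 90-day risk | s = 0.5 | s = 1 | s = 2 |
|---|---|---|---|
| 20% | 11.7% | 6.7% | 2.1% |
| 30% | 18.0% | 10.5% | 3.4% |
| 40% | 24.8% | 14.7% | 4.8% |

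The direction is the same throughout. If every event occurred within 28 days, the two proportions would be equal and there would be no bias.

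**Step 4: a related definition.** Protocol section 7.2.2.2 defines a Phase 1a DLT-equivalent toxicity as one occurring after Cycle 1, and SAP section 5.12.2 defers to that definition. Protocol section 10.3.1 counts any period. Under the post-Cycle-1 definition, a patient with exactly 28 days cannot contribute an event at all. The two need reconciling, and the fix below counts both kinds of event.

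**The case against.** The strongest reply is that the count does not choose the dose. It belongs to the general safety analyses, while section 7.2.2.3 rests the RP2D on all the data. The reviewers will also see more than the count. DLT-equivalent toxicities are listed, the AE listing carries start and end dates (SAP 5.12.3), and cycles received and duration of therapy are summarised (SAP 5.12.1). With 3 to 10 patients per dose, a careful reader can see that the newest patients have had about one cycle. The 90-day clause itself speaks of available data, so incompleteness is acknowledged. The trigger is an earliest time, and the sponsor may wait. All of this stands. It makes the defect partly visible, but it does not supply a by-dose summary matched to the 90-day window, and nothing requires the sponsor to wait.

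Later safeguards exist. Protocol section 9.4.2 reviews each 10 of the first 20 expansion patients and pauses accrual at 7 or more events, and the RP2D may be modified in Phase 1b. Those early reviews also come after about one cycle, so they too precede day 90. For the final report the objection largely succeeds: it falls about 52 weeks after the last expansion patient starts, when Phase 1a patients are well past day 90.

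Two stronger readings are tempting, and the documents support neither.

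- **That the highest dose looks safest and the RP2D is pushed upward.** The affected dose is the last enrolled. Section 7.2.2.1 allows de-escalation, re-escalation and added patients, so that dose need not be the highest. Nor does any passage tie the RP2D to this count.
- **That a dose at the 30% target could pass as a 10% dose.** The 30% is the target DLT rate, and section 7.2.2.2 confines DLTs to Cycle 1. A 10% Cycle 1 rate is correctly 10% against that target. The 30% row in Step 3 is only an assumed 90-day risk.

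**Conclusion.** The point holds as a mismatch between the plan's stated interest in 90-day toxicity and its stated by-dose summary at the pre-expansion review. Raw counts at the last-enrolled doses are biased downward relative to equally toxic earlier doses whenever some qualifying toxicity begins after day 28.

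Under a constant 10% hazard per 28 days, the last dose would show between about 10% and 19%, depending on accrual there, against 29% at a dose with 90 complete days. These figures rest on an assumed hazard, assumed accrual and a review held at the earliest permitted time. The documents fix none of these.

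Cycle 1 DLTs and the mTPI-2 decisions use the same 28 days at every dose and are not affected. An influence on the final RP2D is possible but not shown. This is an inexpensive improvement to the RP2D review, not a flaw in the escalation design.

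**What to change.** Keep the timing of the interim. In protocol section 10.3.1 and SAP sections 5.12.2 and 5.18, replace the any-period count used at the RP2D review with the following, by dose:

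- First DLT or DLT-equivalent toxicity within 90 days of first dose, with the time origin stated.
- Cumulative incidence to day 90, censored at the end of AE observation. Death that is not itself a qualifying toxicity is a competing event, since the entry criterion on life expectancy is only 12 weeks or more.
- The number of patients still under observation at days 28, 56 and 90, printed beside the raw count.

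Reconcile the DLT-equivalent definition in section 7.2.2.2 with the counting rule in 10.3.1 at the same time.

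The cost is one extra table. AE start dates are recorded, and all AEs are collected through the 90-day follow-up visit after treatment stops. The method cannot create follow-up that has not happened: with 3 to 10 patients per dose, the day-90 value at the newest dose will be imprecise or not reached. Showing that to the people choosing the dose is the main gain.
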